6.3. Treatment Assessments

6.3.1. Treatment Visits (Weeks 4 – 48)

The following evaluations are to be completed at the end of Weeks 4, 8, 12, 16, 24, 36 and 48 unless otherwise specified.

All study visits are to be scheduled relative to the Day 1 visit date. Study visits are to be completed within ± 2 days of the protocol-specified visit date through Week 16 and completed within ± 6 days of the protocol-specified visit date through Week 36, unless otherwise specified. The visit window at Week 48 will be ± 6 weeks of the protocol-specified visit date, which coincides with the Week 48 statistical analysis window for HIV-1 RNA. For the purposes of scheduling the Week 48 visit, a ± 6 day window of the protocol-specified visit date should be used.

Regularly scheduled evaluations will be made on all subjects whether or not they continue to receive study drug.

Note: At the Week 16 visit, the only assessments to be completed are:

- Review of AEs and changes in concomitant medications
- Blood sample collection for the following laboratory analyses:
 - Plasma HIV-1 RNA
 - Plasma sample storage for safety and virology testing
- Document study drug dispensation and accountability for all study drug dispensed.
- Questionnaire: Subject is to read questionnaire by her/himself and write/mark answers directly onto questionnaire.
 - Visual Analog Scale (VAS)

For all other visits, please complete the following:

- Review of AEs and changes in concomitant medications
- Complete physical examination (**Weeks 24 and 48**) (urogenital/anorectal exams will be performed at the discretion of the Investigator)
- Symptom-directed physical examination as needed (**Weeks 4, 8, 12 and 36**)
- 12-lead ECG performed supine (**Week 48 only**)
- Vital signs (blood pressure, pulse, respiration rate, and temperature), including weight
- Urine collection for the following laboratory procedures:
 - Urinalysis and urine chemistry
 - Urine pregnancy test (females of childbearing potential only); positive urine pregnancy tests will be confirmed with a serum test. If the test is positive, the subject will be discontinued.
 - Urine sample storage for possible additional clinical testing
- Blood sample collection for the following laboratory analyses:

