6.4. Post-treatment Assessments

6.4.1. Early Study Drug Discontinuation (ESDD) Visit

If a subject discontinues study drug prior to the Week 48 visit, the subject will be asked to return to the clinic within 72 hours of stopping study drug for the ESDD visit. The subject will be asked to continue attending the scheduled study visits through Week 48.

At the ESDD Visit, any evaluations showing abnormal results indicating that there is a possible or probable causal relationship with the study drug, will be repeated weekly (or as often as deemed prudent by the Investigator) until the abnormality is resolved, returns to baseline, or is otherwise explained.

The following evaluations are to be completed at the Early Study Drug Discontinuation Visit:

- Review of AEs and changes in concomitant medications
- Complete physical examination (urogenital/anorectal exams will be performed at the discretion of the Investigator)
- 12-lead ECG performed supine
- Vital signs (blood pressure, pulse, respiration rate, and temperature), including weight
- Urine collection for the following laboratory procedures:
 - Urinalysis and urine chemistry
 - Urine pregnancy test (females of childbearing potential only); positive urine pregnancy tests will be confirmed with a serum test.
 - Urine sample storage for possible additional clinical testing
- Blood sample collection for the following laboratory analyses:
 - Chemistry profile: alkaline phosphatase, AST, ALT, total bilirubin, direct and indirect bilirubin, total protein, albumin, bicarbonate, BUN, calcium, chloride, creatinine, glucose, potassium and sodium
 - Estimated GFR, according to the Cockcroft-Gault formula for creatinine clearance
 - Hematology profile: CBC with differential and platelet count
 - Plasma HIV-1 RNA
 - CD4+ cell count
 - Plasma sample storage for safety and virology testing
 - **CCI**

- Questionnaire: Subject is to read questionnaire by her/himself and write/mark answers directly onto questionnaire.
 - Visual Analog Scale (VAS)
 - HIV-TSQc
- HIV-1 genotype/phenotype resistance testing for subjects with unconfirmed virologic rebound with HIV-1 RNA value ≥ 50 copies/mL
- Questionnaire: Subject is to read questionnaire by her/himself and write/mark answers directly onto questionnaire.
 - HIV Treatment Satisfaction Questionnaire Change (HIV-TSQc)
- Study drug accountability

6.4.2. 30-Day Follow-up Visit

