6.8.2. Resistance Analysis at Subjects Last Visit

Subjects with HIV-1 RNA $<$ 50 copies/mL could experience unconfirmed blips of HIV-1 RNA \geq 50 copies/mL at their last study visit. Such subjects will be analyzed for resistance if the unconfirmed rebound happens at Week 48 or at the last visit while taking study drug (or within 72 hours of discontinuation of study drug).

Figure 6-1. Management of Virologic Failure

- a If virologic rebound is not confirmed, the subject will remain on the study drug.
- b If virologic rebound is confirmed, and the HIV-1 RNA is ≥ 50 copies/mL, the HIV-1 genotype and phenotype (reverse transcriptase, protease and integrase resistance) will be analyzed.
- c Based on the results of the genotype/phenotype assays, the subject will remain or discontinue study drug. If genotyping/phenotyping assay fails, a new ARV regimen may be configured at the discretion of the Investigator in consultation with the Medical Monitor.
- d If no resistance detected, HIV-1 RNA will be repeated (2-4 weeks later). Investigator reviews study drug continuation/discontinuation options and discusses with Medical Monitor prior to discontinuation.
- e A new ARV regimen will be configured, at the Investigator's discretion, and the subject will remain in the study.

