### 3.7.3. Selection of Data in the Event of Multiple Records in an Analysis Visit Window

Depending on the statistical analysis method, single values may be required for each analysis window. For example, change from baseline by visit usually requires a single value, whereas a time-to-event analysis would not require one value per analysis window. When a single value is needed, the following rule(s) will be used:

If multiple nonmissing numeric observations exist in a window, records will be chosen as follows:

- For baseline, the last available record on or prior to the date of the first dose of study drug will be selected. If there are multiple records with the same time or no time recorded on the same day, average (geometric mean for HIV-1 RNA and arithmetic mean for others) will be computed for that day.
- For postbaseline visits:

For key efficacy and safety data (ie, HIV-1 RNA level, CD4+ cell count, and CD4%), the latest record in the window will be selected.

For other numeric observations, the record closest to the nominal day for that visit will be selected. If there are 2 records equidistant from the nominal day, the latest will be selected.

If there is more than 1 record on the selected day, the average will be taken (geometric mean for HIV-1 RNA and arithmetic mean for others).

If multiple nonmissing categorical observations (eg, safety ECG results) exist in a window, records will be chosen as follows:

- For baseline, the last available record on or prior to the date of the first dose of the study drug will be selected. If there are multiple records with the same time or no time recorded on the same day, the value with the lowest severity will be selected (eg, normal will be selected over abnormal for safety ECG findings).
- For postbaseline visits, the most conservative value within the window will be selected (eg, abnormal will be selected over normal for safety ECG)

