## 8. PATIENT REPORT OUTCOMES

The Patient reported outcomes (PROs) include: (1) Visual Analogue Scale (VAS) adherence questionnaires; (2) Short Form-36 Version 2 Health Survey (SF-36); (3) HIVTSQs Status version (at Day 1 only)/HIVTSQc Change version (post-Day 1); (4) FACIT-F; (5) EQ-5D. Unless otherwise stated, multiple responses and out of range responses will be set to missing and missing responses will not be imputed. The Safety Analysis Set will be used in all analyses. No inferential statistics will be provided. All reported data will be listed.

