### 8.1. Adherence – Visual Analogue Scale (VAS) Adherence Questionnaire

The VAS adherence questionnaire is a 3-item, self-reported questionnaire that assesses the degree to which ARV medication was taken in the past 30 days.

For the VAS, the subject is asked to describe their adherence to their ARV regimen by using a linear scale (0% – 100%) to indicate what percent of medications was taken in the last 30 days (0% – taken none of prescribed anti-HIV medication, and 100% – taken all doses of prescribed anti-HIV medication). Two additional questions ask how many days the subject has missed medications in the last 30 days and how many days the subject has missed medications in the last 4 days.

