**Table 8-1. List of Items on the HIVTSQ**

Question	Response Options for Status Form	Response Options for Change Form	Subscale
How satisfied are you with your current treatment?	Very satisfied 6 to 0 very dissatisfied	Much more satisfied now 3 to 3 much less satisfied now	General Satisfaction/Clinical
How well controlled do you feel your HIV has been recently?	Very well controlled 6 to 0 very poorly controlled	Much better controlled now 3 to 3 much worse controlled now	General Satisfaction/Clinical
How satisfied are you with any side effects of your present treatment?	Very satisfied 6 to 0 very dissatisfied	Much more satisfied now 3 to 3 much less satisfied now	General Satisfaction/Clinical
How satisfied are you with the demands made by your current treatment?	Very satisfied 6 to 0 very dissatisfied	Much more satisfied now 3 to 3 much less satisfied now	Lifestyle/Ease
How convenient have you been finding your treatment to be recently?	Very convenient 6 to 0 very inconvenient	Much more convenient now 3 to 3 much less convenient now	Lifestyle/Ease
How flexible have you been finding your treatment to be recently?	Very flexible 6 to 0 very inflexible	Much more flexible now 3 to 3 much less flexible now	Lifestyle/Ease
How satisfied are you with your understanding of your HIV?	Very satisfied 6 to 0 very dissatisfied	Much more satisfied now 3 to 3 much less satisfied now	Lifestyle/Ease
How satisfied are you with the extent to which the treatment fits in with your lifestyle?	Very satisfied 6 to 0 very dissatisfied	Much more satisfied now 3 to 3 much less satisfied now	Lifestyle/Ease
Would you recommend your present treatment to someone else with HIV?	Yes I would definitely recommend the treatment 6 to 0 No I would definitely not recommend the treatment	Much more likely to recommend the treatment now 3 to 3 much less likely to recommend the treatment now	General Satisfaction/Clinical
How satisfied would you be to continue with your present form of treatment?	Very satisfied 6 to 0 very dissatisfied	Much more satisfied now 3 to 3 much less satisfied now	General Satisfaction/Clinical

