33) Lipid modifying medication analyses:

- Lipid modifying medication is defined to be the concomitant medication with any concomitant medication class “LIPID MODIFYING AGENTS” and CMDECOD contains wording of “STATIN” in the ADCM dataset.

- Subjects who took lipid modifying medications at study entry refer to the subjects who use of the lipid modifying agents at study day 1 (ie, the first dose date). More specifically, subjects with “Lipid Modifying Agent Use at Study Entry” include those subjects in Safety Analysis Set with: 1) any selected CM record with the start date  $\leq$  the first dose date, and 2) the end date of the selected CM record is ongoing or the end date of the selected CM record  $\geq$  the first dose date.
- Subjects who initiated lipid modifying medications during the study include the subjects in the Safety Analysis Set who didn’t take lipid modifying medications at study entry and met the following criteria: 1) for subjects who permanently discontinued study drug with any selected CM record started after the first dose date and on and prior to the last dose date; 2) for subjects who are still on study drug with any selected CM records started after the first dose date.
- For lipid modifying medications with the start date completely unknown, we assume the start date is on or before the first dose date, lipid modifying medication was considered as being taken at study entry if the end date is not prior to the first dose date (ie, the end date is on or after the first dose date, completely unknown, or ongoing).
- Lipid modifying medications with the start date prior to the first dose date and the end date completely unknown were considered as being taken at study entry.

34) Age for laboratory test reference range will be based on the age at the sample collection date.

35) For figures, if at a visit where n (sample size) for any treatment group  $< 5$ , data for that treatment group will not be displayed at the visit in figure, but all data will be included in the corresponding table summary.

36) For the PRO data, data up to 30 day after the last dose date for subjects who permanently discontinued of study drug will be summarized.

37) For PRO data, unless otherwise stated, multiple responses and out of range responses will be set to missing and missing responses will not be imputed.

Out of range value is determined based on the following table for within-range response values:

SF-36v2 Health Survey:

Question	Response	

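### The 30-day cut-off for patient-reported outcomes lets a HIVTSQc answer about a replacement regimen enter the by-visit tables and displace the ESDD answer about E/C/F/TAF

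*SAP*

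**What the plan says.** - **Cut-off.** For subjects who permanently discontinued, SAP Appendix 5 item 36 summarises "For the PRO data, data up to 30 day after the last dose date". It does not distinguish between instruments or mention a new antiretroviral. SAP Section 8 adds no limit by regimen: "The Safety Analysis Set will be used in all analyses".
- **Follow-up off drug.** Protocol 6.3.1: "Regularly scheduled evaluations will be made on all subjects whether or not they continue to receive study drug". Protocol 6.4.1 asks the subject to return "within 72 hours of stopping study drug for the ESDD visit" and to go on attending scheduled visits through Week 48. For virologic failure, Protocol Figure 6-1 note e says: "A new ARV regimen will be configured, at the Investigator's discretion, and the subject will remain in the study".
- **Questionnaire schedule.** Under Protocol Appendix 2 note r, the HIVTSQc is given at Weeks 4, 24, 48 and ESDD. The VAS is given at Day 1, Weeks 4, 8, 12, 16, 24, 36, 48 and ESDD. Neither is given at the 30-Day Follow-up.
- **What they ask.** The HIVTSQ items name no drug. One reads "How satisfied are you with your current treatment" (SAP Table 8-1). The VAS "assesses the degree to which ARV medication was taken in the past 30 days" (SAP 8.1).
- **Choice between records in a window.** SAP 3.7.3: "For other numeric observations, the record closest to the nominal day for that visit will be selected".
- **Study-drug adherence.** SAP 4.2.2 uses pill counts, with the treatment period ending no later than premature discontinuation.

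**The concern.** A 30-day tail suits safety data, where an event soon after the last dose may still be due to the drug. A question about present treatment is different, because its subject changes on the day the regimen changes. Item 36 nevertheless applies the same tail to it.

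The schedule already collects the answer that is wanted, at the ESDD visit. A scheduled visit within the next 30 days yields a second answer that may concern another regimen. If both fall in one analysis window, the by-visit table keeps one, and SAP 3.7.3 chooses by closeness to the nominal day without regard to which treatment is described.

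The SAP is stricter elsewhere. Snapshot HIV-1 RNA, CD4 count, CD4% and last on-treatment proteinuria stop at the last dose plus 1 day (SAP 6.2.2.3, 6.2.2.6, 6.2.2.7, 7.3.3, 7.3.4). No reason is given for a longer period for treatment satisfaction. At stake is whether the satisfaction summary, and to a lesser extent the VAS summary, describes E/C/F/TAF for the few subjects who stopped it.

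**Working it through.** The plan states no figure on this point, so there is none to reproduce.

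**One record traced through the rules.** Last dose Day 145, ESDD visit Day 147, new regimen started, Week 24 visit Day 168.

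1. Days since last dose at Week 24: 168 − 145 = 23, which is within 30, so item 36 keeps the record.
2. Both records fall in the Week 24 windows: HIVTSQc Days 99–252 (SAP Table 3-5) and VAS Days 141–210 (SAP Table 3-1).
3. Distance from nominal Day 168: ESDD 168 − 147 = 21; Week 24 visit 0. SAP 3.7.3 selects Day 168.
4. The Week 24 HIVTSQc result therefore concerns the new regimen, and the ESDD answer is left to the listing.

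**How often the calendar allows this.** Assumptions: visits on nominal days; last-dose day uniform over Days 1–335. I count the last-dose days with a later scheduled questionnaire 1 to 30 days on.

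- HIVTSQc (Days 28, 168, 336): last-dose Days 1–27, 138–167 and 306–335, so 27 + 30 + 30 = 87. 87/335 = 26.0%.
- VAS (Days 28, 56, 84, 112, 168, 252, 336): last-dose Days 1–111, 138–167, 222–251 and 306–335, so 111 + 30 + 30 + 30 = 201. 201/335 = 60.0%.

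On a narrower count (last-dose Days 5–330, questionnaire 4 to 30 days later, so beyond the ESDD period) the shares are 72/326 = 22.1% for HIVTSQc and 180/326 = 55.2% for VAS.

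**Subjects affected, as upper limits.** N = 64 (SAP 1.3). The discontinuation rate is assumed.

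| Assumed rate | Discontinuers | HIVTSQc (× 87/335) | VAS (× 201/335) |
|---|---|---|---|
| 2% | 1.28 | 0.33 | 0.77 |
| 5% | 3.20 | 0.83 | 1.92 |
| 10% | 6.40 | 1.66 | 3.84 |

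These are upper limits because they treat every discontinuer as staying in follow-up and as being on a new regimen by the visit.

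**The VAS is a weaker case.** It looks back 30 days. With a last dose on Day 60 and the Week 12 visit on Day 84, up to 24 of the 30 recall days are off E/C/F/TAF, so the record mixes regimens. In the narrower count, 75 of the 180 VAS cases (42%) fall 4 to 14 days after the last dose, where most of the recall still covers E/C/F/TAF. With ESDD 2 days after the last dose, only 134/326 (41%) of last-dose days put the ESDD and the later VAS in the same window, which displacement requires.

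**Effect on a mean.** One subject differing by 20 VAS points moves a 64-subject mean by 20/64 = 0.3 points. For the HIVTSQc total (−30 to +30) the most one record could do is 60/64 = 0.94 points, which needs all ten items to go from worst to best.

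**The case against.** The strongest reply is that this is a prespecified convention in descriptive tables. The 30-day limit matches the safety-data rule in SAP Section 7, and these outcomes use the Safety Analysis Set. SAP Section 8 provides no inferential statistics for them, and they are not among the primary or secondary endpoints. All PRO data and all non-study antiretrovirals are to be listed (SAP Section 8 and 7.5.1), so an affected record could be found. This stands as to severity. It does not answer the displacement in the by-visit table, for which the SAP has no flag.

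Three stronger readings are tempting, and the documents do not support them.

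- *The plan reports the VAS as adherence to E/C/F/TAF.* It does not. SAP 8.1 describes adherence to the subject's antiretroviral regimen. The Day 1 value concerns the pre-study regimen, and change from that baseline is summarised, so the measure spans regimens by design. Study-drug adherence is the separate pill count, which is unaffected. What remains is that other HIV medication is prohibited alongside study drug (Protocol 5.4). Post-baseline VAS records on drug therefore do reflect E/C/F/TAF, and off-drug records pooled with them do not.
- *The bias flatters the drug because those who stop are the least satisfied or adherent.* Neither document says so; the direction is unknown.
- *The calendar shares are expected frequencies.* They are upper limits. Protocol 6.4.2 and 6.5 foresee subjects who refuse further visits or withdraw, and the 30-Day Follow-up collects neither questionnaire. The replacement route that the protocol sets out is virologic failure, and Part 1 pure virologic response at Week 12 was 100% (SAP 1.3).

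**Conclusion.** The point holds in a limited form. Followed as written, item 36 and SAP 3.7.3 can place a HIVTSQc answer about another regimen in the Week 4, 24 or 48 summary and remove the ESDD answer about E/C/F/TAF from it. Off-drug VAS records within the 30 days can mix regimens.

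The size is minor: at most about 0.3 to 1.7 subjects for HIVTSQc and about 1 to 4 for VAS over the whole study. This rests on an assumed 2% to 10% discontinuation among 64, uniform stopping days and visits on nominal days. The documents give no discontinuation rate. The 0.94-point shift is a ceiling and should not be read as a likely effect. Subjects who complete Week 48 on drug are unaffected, as is the primary analysis of pure virologic response.

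**What to change.** Amend SAP Appendix 5 item 36 for HIVTSQc and VAS only:

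1. By-visit summaries use records dated before the start of any new antiretroviral, still within the 30-day limit.
2. The ESDD record is always retained, and is selected over any later off-drug record in the same window.
3. Later records are listed with an off-drug or new-antiretroviral flag.

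Keep the 30-day rule for SF-36, FACIT-F and EQ-5D, which are general health and quality-of-life measures.

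Tying the limit to the new antiretroviral is better than a short fixed cut-off. A last dose plus 1 day rule would leave only 3/335 (0.9%) of last-dose days exposed for HIVTSQc and 7/335 (2.1%) for VAS, but it could drop an ESDD questionnaire completed on the second or third day. A plus 3 days rule could still drop a late one, since the 72-hour return is only a request.

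The cost is a short SAP amendment, one date filter and one selection rule, with no new data collection planned. SAP 7.5.1 already provides for coding and listing non-study antiretrovirals where they are collected; the amendment should say how a missing start date is handled. The downside is that a few off-drug records move from tables to listings.

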### 39) Smoking status at baseline

Smoking status at baseline (ie, never smoker, former smoker, and current smoker) will be summarized as part of the baseline disease characteristics. How to classify a subject as never, former, or current smoker at baseline is specified as follows:

- a) First, select only records with *Type of Substance Use* “Cigarettes” or “Cigars”. Records with *Type of Substance Use* “Other” (including chew tobacco, e-cigarettes, etc) will not be considered as smoking.
- b) Second, for each selected substance use record, flag whether it is “Prior”, “Present”, or “Post” relative to the first dose date according to the Algorithm below.
- c) Finally, (1) the subject will be flagged as “Never smoker”, if the subject has no record with *Type of Substance Use* “Cigarettes” or “Cigars” or all selected records have a flag of “Post”; (2) the subject will be flagged as a “Former” smoker, if any selected records has a flag of “Prior” and no record of “Present”; (3) Otherwise, the subject will be flagged as a “Current” smoker, if any selected records has a flag of “Present”.

	Selected Substance Use Records							
Prior	No	No	Yes	Yes	Yes	No	No	Yes
Present	No	No	No	No	Yes	Yes	Yes	Yes
Post	No	Yes	No	Yes	No	No	Yes	Yes
Smoking Status	Never	Never	Former	Former	Current	Current	Current	Current

